## Observational Registry Study for Symbotex™ Composite Mesh in Ventral Hernia Repair

### Background

An abdominal wall hernia is an abnormal protrusion of the contents of the abdominal cavity or of pre-peritoneal fat through a defect or weakness in the abdominal wall. Repair of abdominal wall hernia is one of the most common procedures performed by surgeons.

Until the 1990s, the fascia-duplication and the fascia-adaptation were the “gold standard” in ventral hernia repair. Because of this unacceptably high recurrence rates after simple reconstruction and the development of new tissue-compatible, prosthetic materials, many surgeons share the opinion that an additional strengthening of the frontal abdominal wall by implantation of allo- and autoplasmic material should be obligatory. According to DEN HARTOG et al Cochrane review [1] there is good evidence that mesh repair is superior to suture repair in terms of recurrences.

As pointed out by ROBINSON et al [2] ideal mesh has been sought since prosthetic materials for hernia repair were first introduced in the 1950s. Authors have generally agreed on several properties of this theoretically ideal mesh:

- be strong enough to withstand physiologic stresses over a long period of time
- conform to the abdominal wall
- promote strong host tissue ingrowth, which mimics normal tissue healing
- resist the formation of bowel adhesions and erosions into visceral structures
- not induce allergic or adverse foreign body reactions
- resist infection
- be non-carcinogenic

There is little agreement or consensus in the literature as to the ideal approach for this difficult problem. In recent years population based studies have provided better data on the true failure rates associated with the various herniorrhaphies [3].

The use of meshes became popular during the 20th century following several studies which showed recurrence rates significantly lower than suture repairs (approximately 10% of recurrence for mesh repairs against 25 to 55% for suture repairs) [4].

According to a review of the literature pooling recurrence data from 2,559 patients, the global recurrence rate varies between 0 and 6% for Parietex™ Composite Mesh at a mean follow-up of 26.1 months.

As described in the literature, the worst recurrence rate following incisional hernia repairs using synthetic meshes by laparoscopic and open approach, is 5.9 % [5] and 5.6 % [6] respectively.

Within 10 years, the tension repairs were outnumbered by tension-free, mesh-based techniques, and these latter hernioplasties now dominate hernia repair in the marketplace [7]. Literature demonstrates prosthetic repair as the best solution even though no consensus is currently established regarding the ideal technique (choice of mesh, surgical technique, and implantation site). Currently, the gold standard for ventral hernia repair according to many surgeons [8],[9],[10],[11] is the Rives Stoppa retro-rectus repair. However, open intraperitoneal technique (the mesh is placed behind all layers of the abdominal wall including the parietal peritoneum [12]) could be an alternative to a retromuscular repair [13]. In this technique, where one side of the mesh faces the abdominal wall, and the other side is in contact with the viscera, hernia repair requires minimizing tissue attachment properties or two-sided (i.e. composite) mesh. Parietex composite mesh (first generation) available since 1998 has become one of the most effective mesh when an intraperitoneal placement is required [14, 15].

Symbotex™ composite mesh is intended for the reinforcement of abdominal wall soft tissue where a weakness exists, in procedures involving primary abdominal wall and incisional hernia surgeries.

Symbotex™ composite mesh is made out of a three-dimensional monofilament polyester textile, which is covered with an absorbable, continuous and hydrophilic film on one of its sides. This film is made up of a mix of collagen from porcine origin and glycerol. The non-absorbable three-dimensional polyester mesh provides long term reinforcement of soft tissues. On the opposite side, the absorbable hydrophilic film minimizes tissue attachment to the mesh in case of direct contact with the viscera. Symbotex™ Composite Mesh was developed based on the Parietex™ Composite (PCO) and Parietex Optimized Composite (PCOX) design and collagen technology for minimizing tissue attachment to the mesh in case of direct contact with the viscera.

In addition, Symbotex™ Composite has been specifically designed for ease of use for example:

- ✓ Green flap for helping to visualization of the fixation area
- ✓ Presence of green marking for orienting and placing the mesh; the green drop-shaped marker in the center of the mesh helps the orientation and placement of the mesh to the medial line of the body.
- ✓ Mesh transparency for improved anatomy visualization during placement
- ✓ Conformability of textile for position against the abdominal wall.

In order to assess the clinical outcomes following the use of Symbotex™ Composite Mesh in primary abdominal wall and incisional hernia repair, this observational registry study has been initiated.

## **1. Study Objectives**

The aim of this Observational Registry Study is to assess the short- and long-term clinical outcomes following the use of Symbotex™ Composite Mesh in primary and incisional

abdominal wall hernia surgeries by open or laparoscopic approach, according to the Instruction for use (IFU) (Appendix B).

One hundred consecutive, adult patients scheduled for primary and incisional abdominal wall hernia surgeries using Symbotex™ Composite Mesh will be reported in the Club Hernie online database, with standard data captured of all preoperative, perioperative and post-operative data, for patient's outcomes measurements.

### **1.1 Primary Objective**

Evaluate the incidence of peri-operative and post-operative complications, with post-operative evaluations occurring, at discharge , 1 week (D1 and D8 follow up), 1 month (D30 follow up), 1 Year and 2 Year follow up after primary and incisional abdominal wall hernia surgeries using Symbotex™ Composite Mesh by open or laparoscopic approach (such as anticipated device related complications such as pain, recurrence, complications related to adhesions, wound complications, other postoperative complications, SAE...).

### **1.2 Secondary Objectives**

Description and assessment of the use of Symbotex™ Composite Mesh for primary and incisional abdominal wall hernia surgeries (surgical techniques, description of dissection, mesh handling, ease of use, surgeon's satisfaction, Quality of life and patient satisfaction...).

## **2. Study Design and Methodology**

This is an observational multicenter registry Study.

### **2.1 Definition**

According to MEDDEV 2.12.2 rev 2 for post-market follow up studies,

Device Registry: An organized system that uses observational study methods to collect defined clinical data under normal conditions of use relating to one or more devices to evaluate specified outcomes for a population defined by a particular disease, condition, or exposure and that serves predetermined scientific, clinical or policy purpose(s).

### **2.2 Scope**

One hundred consecutive adult patients scheduled for primary and incisional abdominal wall hernia surgeries using Symbotex™ Composite Mesh will be reported in the Club Hernie database in real time.

A working group of hernia surgeons, under the auspices of the Club Hernie Society board, have created a French Registry of Abdominal Wall Hernias called Club Hernie. The Club Hernie is a non-profit organization created in 2009, currently including 30 French surgeons' members, with the aim to improve the healthcare treatments in parietal surgery by an assessment of surgical practices, promoting research in abdominal wall surgery using an internet database open to surgeon members to monitor their own hernia practice and outcomes.

This online database consists of a systematic and consecutive data entry of all patients treated for Inguinal Hernia and Ventral Hernia by the 30 French surgeon members, with standard data captured of all preoperative, perioperative and post-operative data.

Covidien is contracting with Club Hernie to act as a authorized representative to perform sponsor's clinical study-related duties and functions, such as implementation and conduct of this observational registry study.

The Club Hernie database will be used for the 100 patient registry from the Club Hernie surgeon members using Symbotex™ Composite Mesh. The Club Hernie database is free for use by surgeons. Only Hernia Club surgeon members are allowed to get an account for the database, protected by identifier and password. The surgeon members having signed the Quality Charter are committed to respecting its principles Club Hernie surgeon members participating in the study will be surgeon members using Symbotex™ Composite Mesh for primary abdominal wall and incisional hernia surgeries according to their current therapeutic practice.

The database is required to be completed anonymously. Therefore, it does not contain any patient data such as name, date of birth, social security number or address of the patient.

One hundred patients will be followed using the online database for registration and patient outcome measurements, including pre-operative, operative, discharge, post-operative course (D1 and D8 follow up), 1 month (D30 follow up), 1 Year and 2 Year follow up. The pain nurses will carry out the pain evaluation on the day of surgery (D0) and on postoperative day 1 (D1) (by phone call in case of day surgery). Pain on day 8 is assessed either during clinical exam or by phone if the patient is already discharged. Patients will be given an appointment for a clinical visit on day 30 (D30 follow up). The post-operative visit at 1 month (D30 follow up) is the standard of care for patient follow up following primary abdominal wall and incisional hernia surgeries.

For long-term follow up, two sets of self-administered QOL questionnaires will be administered by phone call at 1 Year and 2 Year follow-up.

Follow up by phone questionnaires will be performed by a Clinical Research Associate mandated by Club Hernie, independent from the operative surgeons

The Clinical Research Associate will enter into the database answers from the patient-based self-assessment questionnaires.

The answers will be registered without any medical adjustment into the database. The patients who complain of any trouble will be invited to have a clinical visit at the surgeon's office. The correlation between the patient's answer and clinical assessment and physical examination will then be determined.

A patient will be considered lost to follow-up after 5 failed attempts of meticulous postal reminders and phone calls at various times, therefore minimizing the non-response bias.

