## **6. Statistical Methods**

### **6.1 Sample Size Calculation**

As described in the literature, the worst recurrence rate following incisional hernia repairs using synthetic mesh by laparoscopic and open approach, is 5.9 % [5] and 5.6 % [6] respectively.

Assuming a 95% confidence interval, a recurrence rate of 5.9 % with a +/- 5% precision, N=86 patients are needed for the Evaluable Population. Anticipating a 15% lost to follow up at 24 months, we plan to recruit a *minimum* of 100 patients for this observational registry as the Evaluable Population. Patients that are lost to follow-up or that withdraw consent will not be replaced.

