### **Statistical Analysis Plan Summary**

The analysis will be performed for primary and secondary endpoints, all data will be analyzed, according to the methods previously described in the general considerations section.

- 1) Descriptive Analysis of patients registration and outcomes measurement
- 2) Baseline and Demographic Data Analysis
- 3) Operative Data Analysis
- 4) Primary endpoints measured within 1month, 1 Year and 2 Year follow-up
  - a. Peri-operative complications
  - b. Post-operative complications such as anticipated device related complications as pain, recurrence, complications related to adhesions, wound complications, other postoperative complications, SAEs...
  - c. All complications
- 5) Secondary endpoints analysis during the whole follow-up
  - a. Surgical technique and mesh fixation
  - b. Operative time descriptive analysis
  - c. Ease of use / mesh manipulability assessment by surgeons
  - d. Length of hospital stay analysis
  - e. Quality of life and patient satisfaction analysis
  - f. Surgeon satisfaction

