#### POSSIBLE COMPLICATIONS

The possible complications associated with the use of Symbotex™ composite mesh are those typically associated with surgically implantable mesh: seroma, hematoma, recurrence, adhesions, fistula formation, infection, inflammation, chronic pain, and/or allergic reactions to the components of the product.

Potential events associated with state of the art mesh with similar indication may include: organ injury (including bowel and visceral injury), trocar-site herniation, bowel obstruction and urinary retention (related with the use of anesthetics).

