### **2- Do you have a new hernia or bulge?**

- No
- yes (if so Operated side; Scar region; other side; both side, elsewhere (specify))

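### Agreement between phone answers and examination at 1 and 2 years can be known only for complainers who attend, and the 2-year recurrence rate may miss silent recurrences

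*Protocol*

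**What the plan says.** Recurrence belongs to the primary endpoint at 1 and 2 years. The Statistical Analysis Plan Summary in section 6.2 lists it under: "Post-operative complications such as anticipated device related complications as pain, recurrence, complications related to adhesions, wound complications, other postoperative complications, SAEs". It is also the only quantity used to size the registry (section 6.1): "Assuming a 95% confidence interval, a recurrence rate of 5.9 % with a +/- 5% precision, N=86 patients are needed for the Evaluable Population". Section 6.1 continues: "Anticipating a 15% lost to follow up at 24 months, we plan to recruit a" minimum of 100.

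The last clinic visit planned for everyone is at D30. At 1 and 2 years all patients are reached by phone with a self-assessment questionnaire (sections 2.2, 5.7 and 5.8). The direct recurrence item is Appendix C, item 2 of the 1- and 2-year form: "Do you have a new hernia or bulge". A yes is followed by a location field. Item 1 (firmness of the abdomen) and item 9 (re-operation) also bear on recurrence.

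On handling the answers, section 2.2 says: "The answers will be registered without any medical adjustment into the database". On examination: "The patients who complain of any trouble will be invited to have a clinical visit at the surgeon's office". The next sentence says that the correlation between the patient's "answer and clinical assessment and physical examination will then be determined". Sections 5.7 and 5.8 add that complications and the VAS score are recorded at such a visit. Section 7 states that the study requires no visits beyond routine care.

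**The concern.** A correlation between answer and examination needs both measurements in patients who complain and in patients who do not. The protocol fixes who is examined, and patients without a complaint are left out. Section 2.2 therefore announces a comparison that the design can support only in a selected subset, and it does not limit the statement to that subset. If the result were reported as evidence that the phone questionnaire is valid for the cohort, it would claim more than the data can show.

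The same gap affects the recurrence rate. No planned source after D30 would normally reveal a recurrence in a patient who notices nothing or mentions nothing. The protocol also does not say whether the answer or the examination decides when the two differ, or how a report is classed when the invited patient does not attend. The planned precision of 5 points covers sampling error only.

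**Working it through.** **1. The plan's own figure.** Inputs from section 6.1: p = 0.059, half-width d = 0.05, 95% two-sided interval.

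n = 1.96² × p(1 − p) / d² = 3.8415 × 0.059 × 0.941 / 0.0025 = 85.3, rounded up to 86. This reproduces.

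With 15% loss, 100 recruited leaves 100 × 0.85 = 85 evaluable, with a half-width of 5.01 points. That is close enough to the target and is not at issue. About 85 × 0.059 = 5.0 recurrences are expected.

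**2. What can be estimated from the examinations.** The counts here are assumed for illustration. Of 85 patients, 25 complain and all attend. Six of them answered yes to item 2, and 4 of these are confirmed. Nineteen answered no, and 1 has a recurrence on examination. The other 60 do not complain, answer no and are not examined; m of them have a silent recurrence.

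Among the 25 examined, everything can be calculated. The proportion confirmed among yes answers is 4/6 = 67%, and phi = (4×18 − 2×1) / √(6×19×5×20) = 0.66.

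For the cohort, the 2×2 table is a = 4, b = 2, c = 1 + m, d = 78 − m. Then sensitivity = 4/(5 + m), negative predictive value = (78 − m)/79, and phi = (ad − bc)/√[(a+b)(c+d)(a+c)(b+d)].

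| Silent recurrences m | True rate (5+m)/85 | Sensitivity | Negative predictive value | Cohort phi |
|---|---|---|---|---|
| 0 | 5.9% | 80% | 98.7% | 0.71 |
| 1 | 7.1% | 67% | 97.5% | 0.64 |
| 3 | 9.4% | 50% | 94.9% | 0.54 |
| 5 | 11.8% | 40% | 92.4% | 0.47 |

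The observed data are identical in all four rows, so they cannot tell the rows apart. No later analysis choice supplies the missing examinations. If some invited patients do not attend, the subset shrinks further.

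**3. Effect on the rate.** Let s be the share of true recurrences that are detected. The protocol gives no value; 60% to 90% is assumed. Expected observed rate = true rate × s; expected number missed = 85 × true rate × (1 − s).

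- True 5.9%, s = 0.9: 5.3% observed, 0.5 missed.
- True 5.9%, s = 0.8: 4.7% observed, 1.0 missed.
- True 5.9%, s = 0.6: 3.5% observed, 2.0 missed.
- True 10%, s = 0.6: 6.0% observed, 3.4 missed. This looks like the planning value.

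**4. Bias against sampling error.** At a true 5.9% the shift is 0.6 to 2.4 points, below the 5-point half-width. Coverage of the exact 95% interval at n = 85 is 98% with s = 1 and still 95% with s = 0.6. At a true 10% it falls from 96% with s = 1 to 76% with s = 0.6.

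**5. Weight of one unresolved report.** 1/85 = 1.2 points, about a fifth of 5.9%.

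**The case against.** The strongest case on the other side is that this is a descriptive registry under normal conditions of use. Phone follow-up with complaint-triggered visits is a deliberate choice, and an analysis plan is still to be written. The word *then* in section 2.2 can be read as limiting the comparison to patients who come to a visit, and the protocol claims no sensitivity or cohort-level validation. Storing answers unaltered, entered by someone independent of the surgeons, protects them from surgeon influence. The size of any bias rests on an assumed detection range and, at a true 5.9%, stays within sampling error.

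Much of this stands, and it rules out four stronger readings that a reader might infer:

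- *That no negative answers are examined and only a positive predictive value exists.* The trigger is any trouble, which is wider than a bulge. Patients with pain or discomfort who deny a bulge are also invited, so agreement can be computed within that group.
- *That recurrence rests on phone answers alone, or that a yes refuted on examination still counts.* Sections 5.7 and 5.8 list complications as a separate data item and record them at the triggered visit. No text says that a refuted yes remains a recurrence.
- *That silent recurrences are counted as none by rule.* The protocol does not say so. They would usually go unseen because no planned source looks for them, although routine care or the re-operation item may reveal some.
- *That hernias elsewhere inflate the rate.* The instructions for use do list "trocar-site herniation" apart from recurrence, but item 2 already records location, so such cases can be separated.

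What the objection does not remove is that section 2.2 states the comparison without restricting it. Who is examined is fixed in the protocol, so the analysis plan cannot repair this.

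**Conclusion.** The point holds in limited form. Agreement between answer and examination can be obtained only among complainers who attend. Cohort-level correlation, sensitivity and negative predictive value are not identified; that follows from the examination rule alone and needs no assumed figure.

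The 2-year recurrence rate may be too low, by 0.6 to 2.4 points at a true 5.9% if 60% to 90% of recurrences are detected. That size depends wholly on the assumed range. It is modest beside the 5-point precision at the planning rate, and more serious if the true rate is nearer 10%. The data remain usable. What should change is the stated comparison and how the recurrence rate is labelled and broken down.

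**What to change.** **Section 2.2.** Replace the correlation by the proportion clinically confirmed among complainers who were examined, with the numbers invited and attending. Make no claim about the validity of the questionnaire for the cohort.

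**Section 6.2.** Report two recurrence rates:

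- patient-reported: yes to Appendix C item 2 located at the operated side, both sides or the scar region, or a re-operation for recurrence;
- clinically confirmed on examination.

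Show reported but unexamined cases both ways, counted as recurrences and then as non-recurrences. List hernias elsewhere separately, using the location field already in item 2. State that the rate reflects reported recurrence and may miss silent ones. *Reported* is a better label than *symptomatic*, because item 2 asks about a bulge whether or not it causes symptoms.

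**Cost.** A few sentences, an extra table row and a rate that may look slightly less favourable. No visits are added, so section 7 is unaffected. The change finds no additional silent recurrence; it makes the limit visible.

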### **2.3 Monitoring procedures**

No source data verification will be done.

Quality data control of all data captured into the online database will be performed by coherence analysis by Club Hernie authorized representative.

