### **5.8 2 year follow-up**

- QoL and patient satisfaction Questionnaire (Appendix C)
- Post-operative complications (including SAEs)
- Pain assessment measured with VAS score\*

Follow-up at 2 year: All patients will be contacted by phone in order to complete a self-assessment questionnaire.

\*Patients who complain of any trouble will be invited to have a clinical visit at the surgeon's office. Post-operative complications and VAS score will be recorded.

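### Section 2.2 classes patients as lost on failed contact alone, with no stated vital-status or record check, so deaths and other SAEs in unreachable patients may go uncaptured

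*Protocol*

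**What the plan says.** The rule is in Protocol section 2.2: "A patient will be considered lost to follow-up after 5 failed attempts of meticulous postal reminders and phone calls at various times", followed by the claim that this has the effect of "therefore minimizing the non-response bias". No further step is described between the failed attempts and the classification.

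The surrounding text sets the context:

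- Long-term contact is made by someone outside the surgical team: "Follow up by phone questionnaires will be performed by a Clinical Research Associate mandated by Club Hernie, independent from the operative surgeons" (section 2.2).
- Clinical review at 1 and 2 years depends on the patient being reached and reporting a problem: "The patients who complain of any trouble will be invited to have a clinical visit at the surgeon's office" (section 2.2, repeated in substance in sections 5.7 and 5.8).
- On monitoring: "No source data verification will be done" (section 2.3).
- The primary objective (section 1.1) counts complications up to 2 years and includes "wound complications, other postoperative complications, SAE". Sections 5.7 and 5.8 list complications with SAEs at both late time points.
- Section 6.1 plans for the loss: "Anticipating a 15% lost to follow up at 24 months", with no replacement of lost patients.

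**The concern.** Repeated letters and calls reduce casual non-response. They do nothing for a patient who has died, and little for one who is in hospital or in institutional care. Those are the patients whose outcome matters most for a safety endpoint, and under the stated definition they cannot be told apart from patients who ignore the phone. The reason for non-response can then be the outcome itself, and further attempts do not repair that.

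The questionnaire in Appendix C does ask about a new bulge and about re-operation at 1 and 2 years, but only a patient who answers can report either. The operating surgeon's file may already hold the missing fact, yet no section sends the unanswered case back to it, and with no source data verification no later step is planned that would reveal the gap.

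At stake is the completeness of late SAEs in the primary endpoint, and a statement in the protocol that non-response bias has been dealt with when the rule does not show it.

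**Working it through.** **1. The plan's own figures.** Section 6.1 gives a rate of 5.9%, precision of ±5 points, a 95% interval, 86 evaluable patients, 15% loss and a minimum of 100 recruited.

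- n = 1.96² × 0.059 × 0.941 / 0.05² = 85.3, rounded up to 86. This matches.
- 86 / 0.85 = 101.2, so 102 against the stated minimum of 100. With 100 recruited, 100 × 0.85 = 85 remain, and the half-width is 1.96 × √(0.059 × 0.941 / 85) = 5.01 points. The difference is immaterial and the sample size is not at issue.

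**2. What the loss could do to the estimate.** Take 85 followed and 15 lost, as planned. Assume 5 events among the 85, so 5/85 = 5.88%, close to the planning rate. Let the event rate among the lost be k times that of the followed. The protocol gives no value for k, so it is varied.

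Overall rate = (5 + 15 × k × 5/85) / 100. Bias of the responder-only figure = 5.88% − overall rate.

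| k (assumed) | Overall rate | Bias of 5/85 (points) |
|---|---|---|
| 0 | 5.0% | +0.9 |
| 1 | 5.9% | 0.0 |
| 2 | 6.8% | −0.9 |
| 3 | 7.6% | −1.8 |

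In whole events, 1, 2 or 3 among the 15 lost give 6%, 7% or 8% overall, a bias of −0.1, −1.1 or −2.1 points.

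If the lost are instead counted as event-free, the reported figure is 5/100 = 5.0%, which is too low as soon as any lost patient has an event.

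**3. Bounds.** No events among the lost: 5/100 = 5%. Events in all 15: 20/100 = 20%. The span of 15 points is wider than the full planned interval of 2 × 5 = 10 points. The upper end is an extreme, not a forecast.

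**4. Is there a back-up in the text?** Sections 2.2, 2.3, 5.7, 5.8 and 8 were compared. Section 2.2 describes systematic entry of post-operative data by member surgeons. Sections 5.7 and 5.8 add a visit for patients who complain. Section 8 sends device-related complications to the company. None of these is linked to the loss rule or triggered by an unanswered contact.

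**5. Side effect of a record check.** If files are searched only for non-responders and only those with an event are moved into the analysis, one found event changes 5/85 = 5.9% to 6/86 = 7.0%, whereas the count over all enrolled is 6/100 = 6.0%. The repair must avoid that upward bias.

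**The case against.** The strongest reply is that the protocol is silent here, not wrong. It does not forbid a record check, and a relative who answers the phone and reports a death is arguably not a failed attempt. Surgeons enter post-operative data as a matter of routine, and a surgeon who knows of a late event could record it. The handling of missing outcomes can be left to the analysis plan that section 6.2 announces.

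Much of this stands, and it limits what may be concluded. A reader might infer four stronger things that the documents do not support:

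- **That deaths and re-admissions are filed as missing data.** No section sets such a rule. The text only leaves these patients inside the definition of loss.
- **That the patient's answer is the sole source of late events, so that re-operations would show as zero.** Surgeon entry and complaint visits are other routes, and Appendix C asks every responder about re-operation.
- **That incidence is biased downward.** With lost patients left out of the denominator, the bias is downward only if they have more events than those followed. With no events among them it is upward by 0.9 points.
- **That a patient missed at 1 year is not tried again.** Section 5.8 answers this: "Follow-up at 2 year: All patients will be contacted by phone in order to complete a self-assessment questionnaire".

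What the reply does not remove is the gap itself. None of the other routes is tied to an unreachable patient. Who is called lost, and after what check, is a data-collection rule that the protocol already fixes. An analysis plan can bound a missing outcome, but it cannot recover a death or a mesh removal that nobody looked up.

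**Conclusion.** The point holds as a risk in a stated data-collection rule. Loss is defined by failed contact alone, no vital-status or record check is stated, and the claim that non-response bias is minimised is not supported by the rule it is attached to. Late deaths and other SAEs in unreachable patients may go uncaptured, and the long-term incidence in the primary endpoint may be underestimated.

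For recurrence, the illustration gives an overall rate between 5.0% and 7.6% for k from 0 to 3, against 5.9% among responders. It rests on exactly 15 of 100 lost, 5 events among the 85 followed, and assumed values of k. The direction is open for recurrence. For death, underestimation is more plausible, because death itself causes non-response and a questionnaire that the patient must answer cannot detect it.

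**What to change.** In section 2.2, extend the rule:

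1. Before a patient is classed as lost at 1 or 2 years, the operating surgeon's existing file is checked for vital status, re-admission, re-operation, recurrence or mesh removal since the last contact.
2. Any event found is entered with its date and flagged as coming from records.
3. Deaths are reported separately from losses. Only patients with no information from either source count as lost at that time point.
4. The statement on non-response bias is deleted or softened.

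Because files are searched only for non-responders, report two figures: incidence among responders, and incidence including record-found events over all enrolled patients. The second treats those still without information as event-free and should be labelled a minimum. Do not add only the event-positive non-responders to the denominator.

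The cost is about 15 file checks per time point (15% of 100; the protocol gives no separate loss for 1 year), a source flag and a few sentences of text. No extra patient visit is needed, so section 7 is respected. There are two drawbacks. Events treated elsewhere may still be missed. The surgeons also enter a follow-up that was meant to be independent of them, which is why the source must be flagged and the responder-only figure kept.
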